##### **6.2.4.1 Recurrence-free survival**

The recurrence-free survival duration will be measured from the start of Vicineum therapy until disease recurrence, progression, or death due to any cause. Recurrence is suspected and/or determined by urine cytology and/or cystoscopic exam and then confirmed pathologically after a TURBT. Positive cytology in the absence of pathologic confirmation is not considered to be a recurrence. Low grade papillary tumor will not be considered recurrent disease.

##### **6.2.4.2 Complete Response Rate for CIS**

In patients with any component of CIS upon study entry, the complete response (CR) rate will be determined at 3 months, 6 months, and 12 months from the start of Vicineum therapy. Complete response will be defined as the absence of CIS upon follow-up biopsies. These rates can be compared to historical rates of CR for CIS at these various time points.

**Abbreviated Title:** Durvalumab & Vicineum for NMIBC

**Version Date:** 05/22/2025

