### 1.2.2.2 Clinical Studies

#### VB4-845-02-I

A Phase 1 trial (VB4-845-02-I) of Vicineum evaluated doses up to 30.16 mg administered intravesically to 64 subjects with Grade 2 or 3, stage Ta or T1 transitional cell carcinoma (TCC) or CIS, either refractory to or intolerant of BCG therapy. No dose-limiting toxicities (DLTs)

were observed. Vicineum was well tolerated, and the majority of adverse events (AEs) were mild. The most frequently reported treatment-related AEs were renal and urinary disorders, with dysuria (14.1%) and hematuria (10.9%) most commonly reported. Of the systemic AEs, fatigue was reported by 7.8% of subjects, while fever/chills and loss of appetite were each reported by 6.2% of subjects. The frequency of treatment-related AEs did not increase with increasing doses of Vicineum. There was 1 serious adverse event reported (death due to cardiac failure), which occurred 3 weeks after stopping study drug; the Investigator assessed the event to be unrelated to Vicineum treatment, attributing it to the subject's long-standing history of cardiovascular disease. Exploratory efficacy assessment at 3 months showed that of 61 evaluable subjects, a complete response (defined as non-positive urinary cytology and either normal cystoscopy or abnormal cystoscopy with negative biopsy) was achieved by 24 subjects (39%). Of the 17 subjects with Tis, 29% achieved a complete response, while complete responses were observed in 44% and 43% of the subjects with T1 and Ta, respectively.

Blood samples for assessing humoral immune reactivity to Vicineum were taken prior to dosing on days 1, 8, 15, 22, 29, 36, and at the final study visit. Antibody titers to the scFv and ETA252-608 portions of the fusion protein (human antihuman antibodies (HAHA) and human anti-Pseudomonas antibodies (HAPA)) were measured using an enzyme-linked immunosorbent assay. HAPA response was more vigorous, as patients developed a measurable titer earlier; the majority of patients exhibited HAPA by day 29, with 77% (47/61) having a measurable titer at final visit. In contrast, only 16% (10/61) of patients had HAHA by the end of the study. HAPA titers were also generally higher, with a mean maximum titer of 20,512 versus 3373 for HAHA responses. A comparison of mean titers of the HAPA and HAHA responses measured in samples taken on the final visit showed no significant difference between responders and nonresponders.

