#### **VB4-845-02-IIA**

A Phase 2 study (VB4-845-02-IIA) evaluated once-weekly instillations of Vicineum 30 mg in two different induction schedules: weekly x 6 weeks or weekly x 12 weeks, followed by up to 3 maintenance cycles (3 once-weekly instillations followed by a 9-week drug-free period) in 46 subjects with histologically-confirmed TCC of the bladder and residual CIS with or without concurrent Ta or T1 who were refractory or intolerant to BCG. Some subjects in the 6-weekly induction arm received a second induction cycle. Forty-six subjects were considered evaluable for response. A complete response (defined as no histological evidence of disease and negative urine cytology at the 3-monthly evaluations) was achieved by 44% (20/45) of subjects, and 16% (7/45) of subjects remained disease-free at the 1-year end-of-study (EOS) assessment. A post-study assessment found that these subjects were still disease-free at 18-25 months. The median time to recurrence was 134 days longer in subjects who received 12 weeks of induction therapy compared to 6 weeks (408 vs 274 days, respectively; log rank test p=0.1708). The most frequently reported treatment-related AEs were renal and urinary disorders, including 50% with dysuria (61% of these were of mild intensity) and 13% with hematuria. Overall, most AEs were of mild severity. There were 3 severe events, all of which resolved without sequelae. No subject discontinued from the study due to AEs and there were no deaths or other serious AEs.

Based on the preliminary positive therapeutic results and favorable tolerability profile, the present Phase 3 trial will evaluate the efficacy of Vicineum induction therapy administered for 12 weeks, and the long-term effectiveness of Vicineum maintenance therapy (up to 24 months treatment in total) in preventing disease recurrence.

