## **2 ELIGIBILITY ASSESSMENT AND ENROLLMENT**

### **2.1 ELIGIBILITY CRITERIA**

#### **2.1.1 Inclusion Criteria**

2.1.1.1 Patients must have histologically or cytologically confirmed by NCI Laboratory of Pathology as high grade non-muscle invasive urothelial (transitional cell carcinoma) of the bladder as follows:

- Carcinoma-in-situ (CIS) with or without papillary tumors

- High-grade Ta or T1 disease based on a biopsy/TURBT performed within 12 weeks of the initial dose of study treatment. If multiple bladder biopsies/TURBTs are required to confirm eligibility, the timing of the last bladder biopsy to the initial dose of study treatment must be within 12 weeks.
- Patients with persistent T1 high grade disease on TURBT following a single induction course of BCG (at least 5 of 6 doses) may also be eligible for this trial provided that the patient is surgically unfit for cystectomy as deemed by the investigator or the patient declines cystectomy.

2.1.1.2 Subjects with BCG unresponsive disease as defined by the Society of Urologic Oncology and the FDA: Subjects must have received at least two courses of intravesical BCG (at least 5 of 6 induction doses of BCG and at least 2 of 3 maintenance doses of BCG under a maintenance regimen or at least 2 doses of a repeat induction course). Please note exception above for persistent T1 disease. There is no upper limit on the amount of prior BCG a subject may have received.

2.1.1.3 Patients who have met eligibility criterion **2.1.1.2** must have received last BCG dose within a year of enrollment.

2.1.1.4 The investigator must document that he/she believes the subject would not benefit from additional BCG treatment at the time of study entry.

2.1.1.5 Age  $\geq$  18 years at time of signing the informed consent form (ICF). Because no dosing or adverse event data are currently available on the use of Vicineum in combination with durvalumab in patients  $<18$  years of age, children are excluded from this study, but will be eligible for future pediatric trials. Furthermore, NMIBC does not occur in children.

2.1.1.6 Eastern Cooperative Oncology Group (ECOG) performance status 0 or 1 ( [Appendix A](#) )

2.1.1.7 Adequate organ and marrow function as defined below:

- Hemoglobin  $\geq$  9.0 g/dL
- Absolute neutrophil count (ANC)  $\geq$  1.5  $\times$  10^9/L ( $> 1500$  per mm^3)
- Platelet count  $\geq$  75  $\times$  10^9/L ( $>75,000$  per mm^3)

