#### **6.2.3 Response Criteria**

Patients will be evaluated every 3 months as per standard of care with cystoscopy. Biopsy will be done at PI discretion pending cystoscopic findings. Any biopsies done will be for clinical reasons to rule out tumor recurrence, however, extra biopsy material if available will be used for research purposes.

Evaluable for toxicity: All patients will be evaluable for toxicity from the time of their first treatment with vicineum or durvalumab. All observed toxicities will be tabulated using CTCAE v5.0.

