#### 6.2.4.3 Disease Progression & Progression-Free Survival

PFS is defined as the duration of time from start of treatment to time of progression or death, whichever occurs first. The duration of progression-free survival is measured from the start of vicineum therapy until progression or death due to any cause. Disease progression is defined as upstaging from a lower stage to a higher stage (e.g., Ta to T1-T4 or T1 to T2-4; CIS to T1 or CIS to T2-T4; or any N+ or M+ in these high grade tumors).

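### Complete response for CIS patients asks only that CIS be absent on biopsy, so T1, T2 or high-grade Ta without CIS, or positive cytology, can score as CR, and the rule is looser than the Phase 2 Vicineum definition

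*Combined protocol and SAP*

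**What the plan says.** **Who is scored.** Section 6.2.4.2: "In patients with any component of CIS upon study entry, the complete response (CR) rate will be determined at 3 months, 6 months, and 12" (all three time points are in months, counted from the first Vicineum treatment). Section 2.1.1 admits "Carcinoma-in-situ (CIS) with or without papillary tumors", so the CR set includes patients with concurrent papillary disease.

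**The rule.** "Complete response will be defined as the absence of CIS upon follow-up biopsies". On use: "These rates can be compared to historical rates of CR for CIS at these various time points". No reference study, rate or test is named.

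**Progression.** Section 6.2.4.3 counts "CIS to T1 or CIS to T2-T4" as progression. Section 3.6.1 ends protocol therapy at progression or high-grade recurrence, but does not say what happens to the response classification.

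**Biopsy.** Section 6.2.3: "Biopsy will be done at PI discretion pending cystoscopic findings".

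**Earlier Vicineum studies (1.2.2.2).** In Phase 2 (VB4-845-02-IIA), CR meant "no histological evidence of disease and negative urine cytology at the 3-monthly evaluations". In Phase 1 (VB4-845-02-I) it was "defined as non-positive urinary cytology and either normal cystoscopy or abnormal cystoscopy with negative biopsy".

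**Analysis.** Section 10.4.3 plans a response rate in evaluable patients with a two-sided 95% confidence interval. It also compares urinary EpCAM between responders and non-responders, and PD-L1/PD-1 changes both between those groups and between CR+PR+SD and PD.

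**The concern.** The rule removes one lesion type from consideration and ignores the rest of the disease. A CIS patient found to have T1 without CIS is a complete responder under 6.2.4.2 and a progressor under 6.2.4.3, at the same visit and on the same specimen. High-grade Ta without CIS, papillary disease persisting from entry and positive cytology also pass.

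Two results depend on the classification. One is the CR rate, which the plan offers for comparison with history. The other is the set of biomarker comparisons in 10.4.3, which need mutually exclusive groups. CR is the only response category that 6.2.4 defines, so nothing else in the plan settles the matter.

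**Working it through.** **1. The rules side by side, for a patient with CIS at entry who is biopsied at follow-up**

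| Finding | CR under 6.2.4.2 | Phase 2 rule | Elsewhere in the plan |
|---|---|---|---|
| No tumor, cytology negative | CR | CR | no event |
| No tumor, cytology positive | CR | not CR | not a recurrence unless confirmed pathologically (6.2.4.1) |
| Low-grade papillary only | CR | not CR | not a recurrence (6.2.4.1, 3.3.2) |
| High-grade Ta, no CIS | CR | not CR | high-grade recurrence ends therapy (3.6.1) |
| T1 or T2, no CIS | CR | not CR | progression (6.2.4.3) |
| CIS present | not CR | not CR | – |

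No section lets progression, high-grade recurrence or cytology override the CR column.

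**2. The historical figures reproduce.** Phase 2: 20/45 = 44.4% (stated 44%), and 7/45 = 15.6% disease-free at one year (stated 16%). Phase 1, Tis subgroup: 5/17 = 29.4% (stated 29% of 17).

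**3. Direction against Phase 2.** A biopsied patient with no disease on histology and negative cytology necessarily has no CIS on biopsy. Phase 2 responders are therefore a subset of 6.2.4.2 responders. Let p be the rate under the Phase 2 rule and m the share of Phase 2-rule non-responders whose biopsy shows no CIS. Then

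rate under 6.2.4.2 = p + m(1 − p) ≥ p.

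The definitional bias is m(1 − p), which is zero or positive.

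**4. Size.** The documents do not give m, so the values below are assumptions.

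| p | m = 5% | 10% | 20% | 30% |
|---|---|---|---|---|
| 44% | 46.8% | 49.6% | 55.2% | 60.8% |
| 40% | 43% | 46% | 52% | 58% |
| 16% | 20.2% | 24.4% | 32.8% | 41.2% |

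Example: 0.44 + 0.10 × 0.56 = 0.496. At p = 44% the inflation runs from 0.05 × 0.56 = 2.8 points to 0.30 × 0.56 = 16.8 points.

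**5. Per patient.** The plan does not give the number of CIS patients. Assuming 10, 15 or 20, one misclassification moves the rate by 1/10 = 10, 1/15 = 6.7 or 1/20 = 5 points. If two of 15 were misclassified (also an assumption), 6/15 = 40% would be reported as 8/15 = 53%.

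**6. Unbiopsied patients.** The rule presupposes a biopsy that 6.2.3 leaves to discretion. With a normal cystoscopy and no biopsy, a patient could be scored CR, non-CR or excluded. Scoring as non-CR pushes the rate down, so the direction is not fixed.

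**7. Against Phase 1.** Phase 1 accepted a normal cystoscopy without biopsy. Occult CIS under a normal cystoscopy with non-positive cytology is CR there but non-CR here if biopsied. The subset argument therefore fails, and no direction follows for the 29% Tis rate.

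**The case against.** **CR carries little weight.** The primary endpoint is safety. The efficacy endpoints given prominence are 12-month recurrence-free survival (1.2) and disease-free survival (10.1). Section 10 never names CR for CIS, and the historical comparison is optional and untested. This stands. A reader might infer that CR is the main efficacy readout for CIS, but no section says so. The flaw affects interpretation, not a decision rule.

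**Progressors are caught elsewhere.** They count in PFS and recurrence-free survival and stop therapy, and 10.4.3 presupposes that CR and PD are exclusive. This is fair, but it shows the intent without supplying the rule. It also leaves the CR numerator uncorrected and does not reach positive cytology.

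**Biopsies may be routine.** The legible schema cells list biopsy at the 21- and 24-month evaluations, the Study Calendar (3.4) lists biopsies every 3 months as indicated, and each maintenance cycle allows recovery time after biopsy. That may make unbiopsied patients fewer. It does not reconcile the schema with 6.2.3.

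**Upward bias in general.** A reader might infer that every historical comparison is biased upward. Only the comparison of biopsied patients with Phase 2 supports this. The 39–40% three-month rates in the Trial update under 1.2.2.2 come with no CR definition in the available text.

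**The interim result.** Section 1.2.3 reports a 12-week response in 5/12 patients, and a reader might infer that it is inflated. Nothing says those 12 had CIS or were scored by 6.2.4.2, and the trial also enrolls Ta and T1 without CIS. No correction to 5/12 can be derived.

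**Imprecision.** Exact 95% intervals for 6/15 and 8/15 (about 16–68% and 27–79%) overlap heavily. This is true, but a wide interval does not remove a definitional bias.

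**Conclusion.** The concern holds as a defect in the stated rule. Section 6.2.4.2 gives a wrong classification for CIS patients with other high-grade disease, and it contradicts 6.2.4.3 when that disease is T1 or higher. It also ignores cytology. Among biopsied patients, the definitional bias against the Phase 2 rate of 44% is zero or upward. Its size cannot be derived: 5 to 10 points per misclassified patient rests on an assumed 20 to 10 CIS patients, and 2.8 to 16.8 points rests on an assumed m of 5% to 30%. The documents do not show that any patient has been misclassified. No direction follows for unbiopsied patients or against Phase 1.

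This should be fixed before the CR rate or the responder comparisons are reported. It does not threaten the primary endpoint.

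**What to change.** For the analysis only, with no change to treatment or follow-up:

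1. In 6.2.4.2, define CR as no high-grade disease of any stage (CIS, high-grade Ta, T1 or higher) with non-positive cytology. State that progression or high-grade recurrence is non-CR.
2. State how evaluable patients with a normal cystoscopy and no biopsy are classed, and reconcile 6.2.3 with the schema and Study Calendar on biopsy.
3. Keep the evaluable set of 6.2.4, which requires re-evaluation, for the main figure. Show missing assessments as non-CR only as a sensitivity analysis.
4. For any historical comparison, name the study, its rate and its CR definition. Also report CR under the Phase 2 definition, in which low-grade disease is non-CR; the rule in item 1 allows low-grade disease, in line with 3.3.2 and 6.2.4.1, and so remains looser than Phase 2.
5. Note that unconfirmed positive cytology remains a non-event for recurrence-free survival under 6.2.4.1, so a patient can be non-CR and still recurrence-free.
6. Re-score patients already assessed, and use the same classification in the comparisons of 10.4.3.

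The cost is a wording change and a re-read of existing cystoscopy, cytology and pathology. Cystoscopy and cytology are already scheduled every 3 months, so no new procedure is needed. The reported CR rate may fall slightly.

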- Sponsor or Manufacturer terminates the study
- The FDA requests that the sponsor terminate treatment of a specific subject or subjects or all subjects
- Subject noncompliance that, in the opinion of the investigator or sponsor, warrants withdrawal; e.g. refusal to adhere to scheduled visits
- Investigator discretion
- Positive pregnancy test or intent to become pregnant or intent to breast-feed or is breastfeeding
- Disease recurrence with high-grade bladder cancer

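### Complete response in CIS patients requires only that CIS be absent on biopsy, so a patient with high-grade Ta, T1 or T2+ tumour but no CIS counts as a complete responder

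*Combined protocol and SAP*

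**What the plan says.** Section 6.2.4 says that evaluable patients have their response classified by the definitions in its subsections. For patients with any CIS component at entry, 6.2.4.2 gives one criterion: "Complete response will be defined as the absence of CIS upon follow-up biopsies". It adds that "the complete response (CR) rate will be determined at 3 months, 6 months, and 12 months", counted from the start of Vicineum, and that "These rates can be compared to historical rates of CR for CIS at these various time points". No historical series is named.

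Neighbouring sections treat other high-grade disease as failure:

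- Section 6.2.4.3 lists "CIS to T1 or CIS to T2-T4" among its examples of progression.
- Section 3.6.1 ends protocol therapy for progression and, separately, for "Disease recurrence with high-grade bladder cancer".
- Section 6.2.4.1 counts pathologically confirmed recurrence as a recurrence-free survival event. It excludes low-grade papillary tumour and positive cytology without pathologic confirmation.

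The background (1.2.2.2) describes two Vicineum series with wider definitions of CR. In the phase 2 study of CIS patients, CR was "defined as no histological evidence of disease and negative urine cytology at the 3-monthly evaluations". In the phase 1 study it was "defined as non-positive urinary cytology and either normal cystoscopy or abnormal cystoscopy with negative biopsy".

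**The concern.** A CR endpoint should identify patients whose bladder is free of the disease under treatment. This one checks for a single lesion type. Inclusion criterion 2.1.1.1 admits CIS with or without papillary tumour, so a patient can enter with both, keep the high-grade papillary component, lose the CIS and be a complete responder. A patient who entered with CIS alone and is upstaged to T1 without residual CIS is a complete responder and a progression at the same visit.

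Two things are at stake. One is the meaning of the CR rate at 3, 6 and 12 months, particularly if it is set beside rates from studies that demanded more. The other is any analysis that uses CR to sort patients. Section 10.4.3 plans to compare PD-L1/PD-1 changes between patients with clinical benefit (CR, PR or SD) and those with PD. If PD is read as progression under 6.2.4.3, the upstaged patient belongs to both groups.

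**Working it through.** **1. The background figure.** The phase 2 response "was achieved by 44% (20/45) of subjects": 20/45 = 0.444, which agrees. The plan gives no null rate, power or sample size for its own CR endpoint, so there is nothing further to reproduce.

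**2. The definitions side by side**, for a patient with CIS at entry whose follow-up biopsies show no CIS:

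| Finding at the visit | 6.2.4.2 | 6.2.4.3 | Confirmed recurrence (6.2.4.1) | Phase 2 definition |
|---|---|---|---|---|
| High-grade Ta | CR | not among the listed examples | yes | not CR |
| T1, entered with CIS only | CR | progression | yes | not CR |
| T2 or higher | CR | progression | yes | not CR |
| Positive cytology, no tumour on biopsy | CR | no | no | not CR |
| Low-grade papillary tumour | CR | no | no | not CR, read literally |

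The first three rows are the problem. The survival endpoints and off-therapy rules record these patients as failures, but nothing in those sections withdraws CR status.

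**3. Direction.** Among patients who have a follow-up biopsy, anyone with no histological disease and negative cytology also has no CIS on biopsy. The strict responders are therefore a subset of the 6.2.4.2 responders. Let p be the strict CR rate and m the share of strict non-responders whose biopsies show no CIS. Then

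apparent CR = p + (1 − p) × m ≥ p.

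**4. Size, by assumption only.** The documents give neither m nor the number of patients with CIS. Take p = 20/45, the one CIS series whose definition is stated, so 1 − p = 25/45 = 0.556:

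| m (assumed) | Apparent CR | Excess over 44.4% |
|---|---|---|
| 5% | 0.444 + 0.556 × 0.05 = 47.2% | 2.8 points |
| 10% | 0.444 + 0.556 × 0.10 = 50.0% | 5.6 points |
| 20% | 0.444 + 0.556 × 0.20 = 55.6% | 11.1 points |
| 30% | 0.444 + 0.556 × 0.30 = 61.1% | 16.7 points |

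Here m pools high-grade non-CIS tumour with positive cytology. The part due to high-grade tumour alone is smaller by an unknown amount. The table shows how the excess responds to m; it does not estimate this trial's bias.

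**The case against.** The strongest reply is that these failures are not hidden. Confirmed high-grade recurrence is a recurrence-free survival event, upstaging to T1 or higher is a progression-free survival event, and both end protocol therapy. The subsection is titled for CIS and may be meant as a CIS-clearance rate. CR has no hypothesis test or decision rule, and the trial's primary purpose is safety. All of this stands and limits the consequences. It does not change what the CR rate measures or stop one patient being both CR and progressed.

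A second reply is that leaving out cytology is deliberate. Section 6.2.4.1 requires pathologic confirmation before a positive cytology counts as recurrence, and a biopsy-based CR fits that approach. This also stands. The omission of cytology is a problem of comparability, not an error in itself.

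A reader might infer more than the documents support:

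- *That the plan designates the phase 1 and phase 2 series as comparators.* Section 6.2.4.2 allows comparison with history but names no study. The link is an inference; these are the series whose CR definitions appear in the text.
- *That the 39–40% three-month rate in the later phase 3 update is a strict benchmark.* The available text gives no CR definition for it.
- *That every response analysis in 10.4.3 is contaminated.* That section does not say that response means the CIS-only CR. Patients with Ta or T1 disease alone are eligible, and 6.2.4.2 cannot classify them.
- *That the interim 12-week figure of 5/12 is inflated.* The text before the dose justification does not say how that response was defined or whether those patients had CIS.

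**Conclusion.** The definition in 6.2.4.2 is wrong as written for high-grade disease other than CIS: it counts as complete responders patients whom 6.2.4.3 or 3.6.1 treats as failures. Its effect on the CR rate runs one way, upward, relative to the stricter definitions in the background. That direction assumes the same patients and a follow-up biopsy in each. The size cannot be obtained from the documents; the range of 2.8 to 16.7 points rests wholly on assumed values of m from 5% to 30%.

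This should be corrected, but it does not threaten the trial. CR is a descriptive secondary measure, and the safety endpoint, dose decisions and stated sample size do not depend on it. The effect on 10.4.3 is conditional: it arises wherever CR under 6.2.4.2 is used to label responders among patients with CIS.

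**What to change.** In 6.2.4.2:

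1. Define CR, for patients with CIS at entry, as no high-grade urothelial carcinoma of any stage (CIS, Ta, T1 or higher) at the evaluation. Low-grade papillary tumour does not count against response, in line with 3.3.2 and 6.2.4.1.
2. Report clearance of CIS alone as a secondary line.
3. Also report CR with the added requirement of non-positive urine cytology, and use that version against any series that required it. Keeping it as a separate line avoids conflict with the handling of unconfirmed cytology in 6.2.4.1. Name the series used and note any remaining difference, such as low-grade tumour, which the phase 2 wording would exclude if read literally.
4. State how a patient without a follow-up biopsy is classified. Section 6.2.3 leaves biopsy to the investigator's judgement after cystoscopy, and cystoscopy with cytology does not supply grade or stage.

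In 10.4.3, wherever CR is used to classify responders among patients with CIS, apply the revised definition so that no patient is both CR and PD.

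The cost is wording. Cystoscopy and cytology are already scheduled every 3 months, with biopsies as indicated (3.4), so no new procedure is needed. The downside is a somewhat lower reported CR rate.
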